### 6 STUDY RATIONALE

The FREEDOM study is designed to show that the Connected Catheter is able to effectively drain the bladder and the patient to control voiding function. Measurement of post void residual (PVR) volume will be a key performance parameter in this study. The study is designed to show that the subject's PVR volume with the Connected Catheter is similar to using standard catheter (CIC or indwelling Foley-type catheters) without compromising the safety of the subjects. We expect an improvement in the subject's quality of life with the Connected Catheter once he is used to having the Connected Catheter inside the anterior urethra.

The Connected Catheter does not need to be replaced as often as catheters used for intermittent catheterization, but does not remain in place as long as typical indwelling urinary catheters. It also

provides increased convenience over indwelling urinary catheters as the device does not protrude outside of the body, allowing for sexual activity, and does not require the subjects to carry a drainage bag. It uses two anchoring features, one located in the bulbar urethra and one in the bladder. The Controller allows the subjects to control their voiding while using normal restroom facilities. Additionally, the increased frequency of replacement versus indwelling catheters may decrease the occurrence of UTI in the subjects versus traditional indwelling catheters that may be left in the body for up to 29 days.

## 7 RISK-BENEFIT ANALYSIS

### 7.1 Risk Analysis

Complications and risks that exist for other indwelling urinary catheters may also exist for the Connected Catheter. Section 11.9 contains an extensive list of possible adverse events. The major risks and symptoms are described below.

**Table 7-1: Major Risks for the Connected Catheter**

Risk	Description
Urinary Tract Infection (UTI)	UTI is defined in this protocol as bacteriuria $\geq 10^5$ CFU per mL, plus at least one NIDRR consensus-defined symptom. If infection is suspected, appropriate diagnostic and therapeutic measures should be taken.
Asymptomatic Bacteriuria	The presence of bacteria in the properly collected urine of a patient that has no signs or symptoms of a urinary tract infection.
Bladder Spasms	When the bladder muscle squeezes suddenly without warning, causing an urgent need to release urine. The spasm can force urine from the bladder, causing leakage.
Dysuria	Pain experienced while urinating. Dysuria can be caused by UTI, inflammation of the LUT, sexually transmitted diseases, and more. The operation of the device should not cause pain while voiding. If this occurs, a clinician should evaluate the subject to determine the likely cause and follow the standard of care. If necessary, the device may be removed.
Genitourinary pain	Initial discomfort may occur when first using the device. Pain should be properly evaluated by a clinician and the cause(s) identified. Genitourinary pain can have many causes unrelated to the device itself ranging from enlarged prostate to fibromyalgia to infection. The proper standard of care should be followed once the cause(s) are identified.

Risk	Description
Hematuria	Blood in the urine may be caused by LUT injury, UTI, kidney or bladder stones, enlarged prostate, the device itself (from insertion, removal, migration, improper sizing), and more. During initial use of the device minor hematuria may be observed. If it continues or worsens, then follow the standard of care to diagnose and alleviate the symptom.
Stricture	Hardening of the tissue. May be caused by frequent catheter use and/or false passage.
Urethral Trauma	False passage may be associated with improper and/or frequent catheter use.
Urinary Incontinence	Leaking may occur through or around the catheter if the bladder spasms, or the catheter valve is not closed properly.
Urinary retention	If patient is unable to empty the bladder, then Urinary Retention may occur.
Discomfort	Discomfort is often associated with frequent catheterization.

These complications may occur at any time during (or shortly following) Connected Catheter insertion, usage, or removal, and may require additional medical treatment. All the above medical complications can be easily treated by the standard of care. Each of the above risks is comparable or lower with the Connected Catheter compared to intermittent catheterization in terms of likelihood and severity. In addition to the above risks, there may be other risks that are unforeseen at this time.

## 7.2 Risk Mitigation

Spinal Singularity, Inc. is committed to minimizing the risks to human research subjects in all of its clinical studies, and has taken measures to minimize risk, including the following:

The Gen 2 Connected Catheter System and Accessories have been designed and developed according to Spinal Singularity Inc.'s Product Development Process (PDP), which is utilized in conjunction with a rigorous standard operating procedure (SOP) for Risk Management (including risk mitigation). This Risk Management SOP is based on the industry best-practice standards detailed by EN ISO 14971:2012 ("Application of Risk Management to Medical Devices"). Spinal Singularity, Inc. also maintains detailed procedures (SOPs and DOPs) for Risk Evaluation, Design Controls, and Control of Quality Records.

Pre-clinical performance testing of the Gen 2 Connected Catheter System: the essential functions of the Gen 2 Connected Catheter System (insertion, voiding, sealing, and removal) has been thoroughly tested in a series of design verification and validation tests. Connected Catheter product will not be released by Spinal Singularity, Inc. for investigational clinical use until the Gen 2

Connected Catheter System has passed a defined set of performance and acceptance criteria required for clinical product.

The subject eligibility criteria for participation in this study have been carefully defined to ensure their medical suitability and minimize the risk of complications.

This clinical investigation protocol specifies that the initial insertion and Clinic Assessment of the Gen 2 Connected Catheter System will be performed in a clinical setting, with subjects under direct supervision, where the Connected Catheter device can be immediately removed and any necessary medical care can be administered in the case of any acute medical complications (device-related or otherwise).

This protocol involves close subject monitoring and evaluation at consecutive stages of Connected Catheter performance assessment, with subjects allowed to progress to the Test Phase of the study only if they exhibit good Connected Catheter tolerability and demonstrate the ability to effectively use the Gen 2 Connected Catheter System as trained.

As part of their training to use the Gen 2 Connected Catheter System, subjects will be trained to remove the Connected Catheter using the IR Tool and will be provided with an IR Tool to keep available at all times throughout the Test Phase, in the event that the Connected Catheter must be removed at any time.

During the Test Phase of the Study, subjects will maintain the phone number of the clinic should any adverse events arise. Staff will provide any necessary medical or device-related guidance.

All Study Investigators will be thoroughly trained in this clinical investigation protocol, including the Gen 2 Connected Catheter System and Accessories Clinician Instructions for Use (IFU) and procedural elements of the study.

### 7.3 Potential Benefits

The potential benefits to future patients suffering from chronic Urinary Retention are listed below. For study subjects, similar benefit may be experienced albeit temporary only during the study until the device is commercially available. However, the potential longer-term benefit to the patients suffering with chronic Urinary Retention outweigh the risks of participation in this study.

The benefits when using the Connected Catheter may include, but are not limited to, the following:

[figure not shown]
1. Improvement in the comfort and/or convenience of urinary management while using the Gen 2 Connected Catheter System.
2. Improvement in quality of life related to urinary function and overall social confidence.
3. Reduction in the risk of urinary tract infection, genitourinary injury, and other medical complications associated with the use of standard urinary catheters.
4. A collection bag is not required while using the Connected Catheter.

## 8 CLINICAL STUDY DESIGN

The FREEDOM Study is a prospective, open, single-arm, non-significant risk (NSR) study to be performed in the United States with consecutive enrollment to evaluate the safety and efficacy of the Connected Catheter System in treating subjects with chronic Urinary Retention. All patients

that sign an informed consent form are considered to be part of the intended-to-treat (ITT) population.

The study will be broken up into 4 phases – Eligibility screening, Device Tolerability screening, Connected Catheter use, and Follow-Up. Figure 8-1 shows an overview of the study with the estimated sample size enrolled and treated.

**Figure 8-1: Study and Subject Flowchart**

## 8.1 Study Objective

The objective of this study is to evaluate the safety and essential performance of the Connected Catheter in males with chronic Urinary Retention, both in an acute clinical setting and an extended period of home use.

## 8.2 Screening Phase

The Screening Phase is divided into two phases – Standard Eligibility and Device Tolerability phases. During Standard Eligibility screening, subjects will be evaluated according to the inclusion and exclusion criteria listed in this clinical investigation protocol including assessment of their urinary status using their standard of care management system. Additionally, the subjects will be assessed as outlined in Section 9.2.

Subjects that pass the eligibility screening will enter a 7-day trial period (Device Tolerability Screening) in which they will use the Connected Catheter. They will be taught how to insert and remove the Connected Catheter as well as how to operate the device. Any subject that is unable to demonstrate proficiency in the operation of the device will not continue to the Test Phase of the study. During this time, subjects that use the Connected Catheter will be assessed for any pain or discomfort while using the device. Subjects that are unable or unwilling to complete the days of device use will not continue to the Test Phase of the study.

## 8.3 Test Phase

During this period, the subjects will use the Connected Catheter to manage their chronic Urinary Retention. The subjects will remove the device themselves under supervision of a trained clinician. A new Connected Catheter will be inserted by the subjects under the supervision of a

trained clinician. There will be weekly follow-ups during this period to complete assessments as outlined in Table 9-2.

#### **8.4 Follow-Up Phase**

This phase is 2 weeks long, and the subjects will return to using their previous method to manage their chronic Urinary Retention. There will be weekly phone calls during this period to screen for any signs or symptoms of Adverse Events as outlined in Table 9-2.

### **8.5 Primary Endpoints**

#### **8.5.1 Primary Efficacy**

During each follow-up, and during the initial device insertion and evaluation, the Post-Void Residual (PVR) urine volume will be measured via ultrasound.

A subject will be considered a responder to the device if at least 80% of the subject's available PVR values are:

- a. Less than 50 mL OR
- b. Equal or less than baseline PVR with the standard urinary management system

If a subject drops out before the conclusion of the study after passing the Device Tolerability Screening, their PVR data will still be included in the primary analysis.

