	
h. Bladder stones
 
7. Dependence on an electro-magnetic medical implant (e.g. cardiac pacemaker or implanted drug pump) or external device
 
8. Any unsuitable comorbidities as determined by the Investigator or complications related to use of certain medications
 
9. Any physical or cognitive impairments that diminish the subject's ability to follow directions or otherwise safely use the Gen 2 Connected Catheter System
 
10. Catheter Assessment Tool screening yields unacceptable results

Primary Efficacy Endpoint	
Primary efficacy: Post-void residual urine volume (PVR) with the use of the Connected Catheter
 
A subject is considered a responder to the treatment if a minimum of 80% of their PVR values met the following criteria
 
PVR is <math>\leq</math> 50 mL OR
 
PVR is <math>\leq</math> baseline PVR with the standard of care catheter
 
If a subject drops out before the conclusion of the study after passing the Device Tolerability Screening, their PVR data will still be included in the primary analysis.

Primary Safety Endpoint	Rate of device related SAE
Secondary End Points	
 
1. Successful device insertion, anchoring, and removal
 
2. Successful sealing of the catheter valve
 
3. Quality of life improvement as measured by SCI-QOL Survey
 
4. UTI occurrence rate
 
5. Lower Urinary Tract injury rate
 

Study and Data Management	
Spinal Singularity, Inc.
 
[name]
 
[name]
 
[contact]
 
Fax: + 1 [contact]

Study Safety Monitor	
[name], MD,
 
Professor of Urology and Radiology Chairman,
 
Department of Urology

	University of California, Irvine
--	----------------------------------

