### **8.6 Secondary Endpoints**

The following secondary endpoints will provide additional characterization of the Connected Catheter in the treatment of chronic Urinary Retention and to support potential labeling claims.

1. Successful device insertion, anchoring, and removal
2. Successful sealing of the Connected Catheter valve
3. Quality of life improvement as measured by SCI-QOL Survey and other surveys
4. UTI occurrence rate
5. Lower Urinary Tract injury rate

These endpoints will be analyzed with descriptive statistics and nominal 95% confidence interval.

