### **9.2.5 Voiding Assessment(s)**

Prior to bladder voiding, the research staff will task the patient to locate the Connected Catheter end and assess if any migration has occurred. Next, the subject is to perform bladder voiding using the Controller, and the PVR Volume is then measured and recorded. The subject will remain in the vicinity of Study clinic premises for additional bladder filling and voiding cycles, to be conducted in the same manner without repeating the positioning and sizing assessment. A total of 3 voiding cycles will be performed during the initial insertion visit and twice during each Test Phase visit.

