## **9.4 Test Phase**

The Test phase will require three (3) Exchange Appointments and a final Removal Appointment. Each appointment will assess PVR, voided volume, quality-of-life (QOL), and urinary tract injury, adverse events, medication, and other study assessment. Additionally, the subjects will be asked to fill out a User Experience Survey and Safety and Performance Survey and the device will be evaluated for fit, migration, placement, and removal.

At each exchange visit, the clinic research staff will follow these procedures:

1. Patient Arrival – Vital Signs and other measurements
2. Bladder Volume – Measurement using Ultrasound to ensure at least 200 mL of urine
3. Patient empties bladder – PVR volume measurement using Ultrasound
4. Patient removes Connected Catheter
5. Patient waits for bladder to fill – additional surveys completed
6. Patient inserts new Connected Catheter and bladder emptied – PVR volume measured
7. Patient Departure

For the final device removal visit the clinic research staff will follow these procedures:

1. Patient Arrival – Vital Signs and other measurements
2. Bladder Volume – Measurement using Ultrasound to ensure at least 200 mL of urine
3. Patient empties bladder – PVR volume measurement using Ultrasound
4. Patient removes Connected Catheter
5. Patient completes all surveys
6. Patient departure

Once the patient completes the final device removal visit the patient will enter the follow-up phase.

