## 10 STATISTICAL CONSIDERATIONS

### 10.1 Primary Endpoint Hypothesis

The primary endpoint analysis consists of a one-sided test of the null hypothesis that no more than 60% of users are responders to the device against the alternative that more than 60% of users are responders, as given below:

$$H_0: R \leq 60\%$$

$$H_a: R > 60\%$$

Where,

R = % of users who are responders

In this study, R is estimated as the percent of subjects who are responders, and a subject will be considered a responder to the device if at least 80% of that subject's individual available PVR values are:

- a. Less than 50 mL OR
- b. Equal or less than baseline PVR with the subject's standard urinary management system

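### The primary PVR cut-off is stated two ways, and the responder rule is an unlabelled while-on-device rule under which a man who stops early in the Test Phase can count as a responder on readings taken by Day 7

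*Combined protocol and SAP*

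**What the plan says.** The synopsis names the primary efficacy measure as "Post-void residual urine volume (PVR) with the use of the Connected Catheter". Section 10.1 makes a man a responder if "at least 80% of that subject's individual available PVR values are" under 50 mL or no higher than his baseline on his usual system; 8.5.1 has the same rule. The synopsis instead lets a reading of exactly 50 mL pass.

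On which readings count, 8.5.1 says: "During each follow-up, and during the initial device insertion and evaluation, the Post-Void Residual (PVR) urine volume will be measured via ultrasound". Section 9.2.5 gives the number: "A total of 3 voiding cycles will be performed during the initial insertion visit and twice during each Test Phase visit". Section 9.3 applies the Test Phase assessments at the end of tolerability screening. Section 9.4 says: "The Test phase will require three (3) Exchange Appointments and a final Removal Appointment". It lists two PVR measurements at each exchange visit and one at removal.

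On dropouts, 8.5.1 says of the primary analysis: "If a subject drops out before the conclusion of the study after passing the Device Tolerability Screening, their PVR data will still be included". Sections 9.7.1.1 and 9.7.1.5 likewise use data up to withdrawal. Section 10.3 promises an analysis of dropouts and tipping-point analyses, with no method for either.

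The objective in 8.1 is safety and essential performance "both in an acute clinical setting and an extended period of home use".

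**The concern.** Nothing in the responder rule requires a reading from the Test Phase. A man can pass tolerability screening, give up the device soon afterwards because of pain, migration or device failure, and still enter the one hypothesis test as a success. A reader told that the rate beat 60% could take this to mean that the device drains well and can be used through the four-week Test Phase. The rule supports only the first half of that statement.

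The analyses promised in 10.3 do not clearly close the gap. A man with enough good early readings already has an observed status, so a tipping-point analysis that varies only missing outcomes would leave him unchanged. Section 9.6 asks for the results of tests done at unscheduled visits, but leaves it to the investigator whether to repeat them. A failure that leads to stopping may therefore never produce a PVR value.

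The two cut-offs are a separate and smaller matter, but they concern the primary endpoint and should not be left to the programmer.

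**Working it through.** **Cut-off.** The baseline limb passes a reading equal to or below baseline in every version. If baseline is 50 mL or more, a reading of exactly 50 mL passes whichever cut-off is used. The versions differ only for a reading of exactly 50 mL in a man whose baseline is below 50 mL.

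**Readings by Day 7.** There are 3 at the insertion visit (9.2.5) and 1 or 2 at the Day 7 visit, depending on how 9.3 and 9.4 are read. That makes 4 or 5.

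| Good readings by Day 7 | Failed Test Phase readings | Share passed | Responder at 80%? |
|---|---|---|---|
| 4 | 0 | 4/4 = 100% | yes |
| 4 | 1 | 4/5 = 80% | yes |
| 4 | 2 | 4/6 = 67% | no |
| 5 | 0 | 5/5 = 100% | yes |
| 5 | 1 | 5/6 = 83% | yes |
| 5 | 2 | 5/7 = 71% | no |

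**Full schedule.** Insertion 3, Day 7 1 or 2, three exchange visits at 2 each, and removal 1 (9.4) or 2 (9.2.5, if removal counts as a Test Phase visit). The smallest total is 3 + 1 + 6 + 1 = 11 and the largest is 3 + 2 + 6 + 2 = 13. Reaching 80% takes 9 of 11, 10 of 12 or 11 of 13, so at most 2 may be failed or missed.

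**The plan's own sample size.** 24 × (1 − 0.33) = 16.08, which reproduces the stated minimum of 16. The plan gives no power figure.

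**Exact test.** One-sided, null rate 0.60, level 0.05 (10.1, 10.3). The critical value is the smallest c with P(Bin(n, 0.60) ≥ c) ≤ 0.05.

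- n = 16: P(X ≥ 14) = 0.018 and P(X ≥ 13) = 0.065, so c = 14.
- n = 24: P(X ≥ 19) = 0.040 and P(X ≥ 18) = 0.096, so c = 19. This size applies only if every man entering tolerability screening is analysed; the mITT population is not defined.

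**How far the two scorings can differ.** Assume that men who stay on the device respond at 0.90 (10.2 expects more than 90%) and that d men stop for a device-related reason. The values of d are illustrations. Scored as responders, the chance of success is P(Bin(n − d, 0.90) ≥ c − d). Scored as failures, it is P(Bin(n − d, 0.90) ≥ c).

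| n | d | Stoppers as responders | Stoppers as failures |
|---|---|---|---|
| 16 | 1 | 0.82 | 0.55 |
| 16 | 2 | 0.84 | 0.23 |
| 16 | 3 | 0.87 | 0 (13 men left, 14 needed) |
| 24 | 2 | 0.98 | 0.83 |

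**Missed device-related readings counted as failures.** Take a man whose readings all pass.

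- Stops after both readings at the third exchange visit: 10/11, 10/12, 11/12 or 11/13, all at least 83%. Responder.
- Removes the device at the third exchange visit and has no new one inserted, so only the first reading exists: 9/11 (82%) or 10/12 (83%) passes, but 9/12 (75%) or 10/13 (77%) does not.
- Last visit is the second exchange: 8/11, 8/12, 9/12 or 9/13, all at most 75%. Non-responder.

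The middle case turns on how many readings are scheduled, which 9.2.5 and 9.4 leave open.

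**The case against.** The strongest reply is that the plan does settle the scoring. Available values, retention of dropouts' data and use of data up to withdrawal together give a while-on-device rule that applies whatever the reason for stopping. It suits the rationale in section 6, which is drainage similar to a standard catheter. Tolerability has its own gate in 9.3. Device-related adverse events are summarised under 8.5.2, and 8.6 covers items such as "Successful device insertion, anchoring, and removal" and valve sealing. Section 10.2 concedes limited power and presents the data as a basis for later work. All of this stands. A reader might infer that the plan is silent on stoppers, or that the primary test must score them as failures. The documents support neither: the default rule is there, and changing it is a trade-off that would cut the chance of success from 0.84 to 0.23 in the example with two stoppers at n = 16.

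A reader might also infer an inflated type I error. Suppose the rate of responding and staying on the device is exactly 60%, and all of 1, 2, 3 or 4 stoppers are scored as responders. The test at n = 16 then rejects with probability 0.053, 0.135, 0.299 or 0.558. But the plan's own R would be (9.6 + d)/16, or 66%, 73%, 79% and 85%, all above the null. These figures are not errors of the test as written.

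Nor is the issue clinic against home. Every scheduled PVR reading is taken in clinic, and the first Day 7 reading follows up to a week of use after discharge. The issue is how much of the period of use a man's status covers.

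Finally, the tipping-point wording in 10.3 is broad enough to take in these men. Without a stated method, it does not commit anyone to doing so.

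**Conclusion.** Two points hold. The 50 mL cut-off is inconsistent, with a narrow effect: a reading of exactly 50 mL with a baseline below 50 mL. The responder rule is in effect a while-on-device rule. It is acceptable as a primary analysis, but it is unlabelled and has no prespecified companion showing what happens when device-related stopping counts. As it stands, it can support a statement about PVR while the device is in use by men who pass tolerability screening. It cannot by itself support one about drainage over extended home use.

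At n = 16 one reclassified man can move the result across the significance boundary, from 14/16 (p = 0.018) to 13/16 (p = 0.065). The documents give no rate of device-related stopping in the Test Phase, so the likely size of the effect is unknown. The chances of success shown rest on an assumed 90% response in men who stay and on assumed numbers of stoppers. The facts about the text are certain. This should be fixed before the data are seen.

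**What to change.** 1. State one 50 mL cut-off in the synopsis, 8.5.1 and 10.1.
2. Keep the available-values test as primary, name it a while-on-device estimand, and limit its conclusion to PVR while the device is in use by men who pass tolerability screening.
3. Make the following the stated method for the dropout analysis in 10.3, reported beside the primary result: scheduled Test Phase readings missed after stopping for a device-related reason count as failed readings in the 80% calculation. Code the reason on the End of Study form before analysis. Section 9.7.1.5 already requires the reason to be documented, but the reasons listed in 9.7.1.2 include withdrawal of consent and loss to follow-up, which can hide a device-related cause.
4. Also report responder status from Test Phase readings only.
5. Reconcile the number of scheduled readings per visit between 9.2.5 and 9.4, including the Day 7 and removal visits, so that the 80% denominator in item 3 is fixed.

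The cost is protocol wording, one coded field and minor programming. The primary test and its power do not change. The downside for the sponsor is a supporting result that may be less favourable than the primary one.
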